#### **7.4.2.5 DRC Assessments**

Reasons for EOST failure according to DRC classifications (i.e. because (i) Blood cultures and/or cultures from other sites did not become negative at EOST, (ii) *Candida* infection spread to other sites, (iii) Additional antifungals given, (iv) Patient died, (v) Patient withdrew from study but did not die, or (vi) Other), will be summarized descriptively at the EOST visit for the MITT and PP populations. Once a patient has failed treatment, they are subsequently evaluated only for survival and for relevant safety parameters.

Reasons for relapse, or other reasons for not having an outcome of sustained success at follow-up according to DRC classifications, will be summarized descriptively at 2 and 4 weeks after EOST for the MITT and PP populations. Once a patient has relapsed, or has been assessed as a non-sustained success for any reason, they are subsequently evaluated only for survival and for relevant safety parameters.

Reasons for death according to DRC classifications (i.e. Candidemia/invasive candidiasis probably contributory, candidemia/invasive candidiasis probably not contributory, or not known) will be tabulated for the MITT and PP populations.

Factors that can affect outcome, such as intravascular catheter management (timely removal of lines), will be also be summarized descriptively.

#### **7.4.3 Exploratory Efficacy Endpoints**

Change in serum (1,3)- $\beta$ -D-glucan levels from Baseline (pre-dose) to EOST will be summarized in total with descriptive statistics for the MITT Population.

#### **7.4.4 Other Efficacy Data**

All other efficacy data will be listed by patient.

### **7.5 Pharmacokinetic Assessment**

All pharmacokinetic analyses will be performed by another vendor and described in a standalone PK analysis plan.

### **7.6 Safety Assessment**

Safety data will be summarized based on the ITT/Safety Population.

### **7.6.1 Adverse Events**

AEs will be captured from the date of informed consent through study completion. All AEs will be coded to system organ class and preferred term using the MedDRA, Version 22.0. Treatment-emergent adverse events (TEAEs) are defined as AEs that start on or after the administration of study drug.

An overview of AEs will be provided including counts and percentages of patients (and event counts) with the following:

- Any AEs;
- Any TEAEs (overall and by maximum severity);
- Any study drug-related TEAEs (overall and by maximum severity);
- Any serious AEs (SAEs);
- Any treatment-emergent SAEs (TESAEs);
- Any study drug-related treatment-emergent SAEs (TESAEs);
- Any TEAEs leading to discontinuation of study drug;
- Any study drug-related TEAEs leading to discontinuation of study drug; and
- Any AEs leading to death.

The overview of AEs will be repeated for the subsets of AEs occurring during the treatment period and AEs occurring after the treatment period in the same manner above.

The number and percentage of patients who experienced at least one TEAE will be presented by system organ class and preferred term. Drug-related TEAEs, study drug withdrawals due to TEAEs, and all SAEs will be summarized in the same manner.

Summaries will be provided by worst grade for the number and percentage of patients with TEAEs and for patients with drug-related TEAEs by system organ class and preferred term.

Although a patient may have two or more TEAEs, the patient is counted only once within a system organ class and preferred term category. The same patient may contribute to two or more preferred terms in the same system organ class category.

A list of patients who have SAEs, a list of patients who discontinue from study drug due to TEAEs, and a list of death due to AEs will be provided. All adverse events will be listed.

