4.3 Dosing Criteria

Participants must meet the following criteria to begin dosing:

Confirmed diagnosis of candidemia and/or invasive candidiasis caused by *C. auris* (in a single or mixed *Candida* spp. infection) within <120 hours (for candidemia) or within <168 hours (for invasive candidiasis without candidemia) of the indicative positive blood culture or the indicative positive culture from a specimen sampled from a normally sterile site, plus confirmation that all other eligibility criteria are met, qualify the patient for dosing with APX001. The initiation of the first dose of APX001 must occur within 12 hours of qualification for the study.

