6.3 Screening

Screening procedures must occur within a 120-hour window (for patients with candidemia) or 168-hour window (for patients with invasive candidiasis without candidemia) prior to qualification for the study.

The following procedures will be performed at Screening:

- Obtain informed consent
- Review inclusion/exclusion criteria
- Record medical history
- Record demography information
- Record vital signs, including temperature, blood pressure, heart rate, respiratory rate, oxygen saturation, and weight
- Intravascular catheter management and log of the line changes, to include any catheter tip culture results
- Perform clinical laboratory assessments (serum chemistry, hematology, coagulation, and urinalysis)
- Perform urine pregnancy test (for females of childbearing potential only)
- Collect blood cultures (daily)
- Collect other cultures and histopathology from other sites, as clinically indicated
- Perform imaging tests as clinically indicated to assess the site(s) and extent of invasive candidiasis infection at study baseline
- Record prior/concomitant medications
- Record adverse events

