8 SAFETY ASSESSMENTS

8.1 Adverse Events

An adverse event is defined as any untoward medical occurrence in a clinical investigation subject administered a pharmaceutical product, which does not necessarily have a causal relationship with this treatment. An adverse event can therefore be any unfavorable and/or unintended sign (including an abnormal laboratory finding), symptom, or disease temporally associated with the use of a study drug, whether or not related to the study drug. All adverse events, including observed or volunteered problems, complaints, or symptoms, are to be recorded on the appropriate eCRF.

Adverse events, which include clinical laboratory test variables, will be monitored and documented from the time of informed consent until study participation is complete. Subjects should be instructed to report any adverse event that they experience to the Investigator. Beginning with Day 1 of study drug, Investigators should make an assessment for adverse events at each visit and record the event on the appropriate adverse event eCRF.

Wherever possible, a specific disease or syndrome rather than individual associated signs and symptoms should be identified by the Investigator and recorded on the eCRF. However, if an observed or reported sign or symptom is not considered a component of a specific disease or syndrome by the Investigator, it should be recorded as a separate adverse event on the eCRF. Additionally, the condition that led to a medical or surgical procedure (e.g., surgery, endoscopy, tooth extraction, or transfusion) should be recorded as an adverse event, not the procedure.

Any medical condition already present at Screening should not be reported as an adverse event unless the medical condition or signs or symptoms present at Baseline changes in severity or seriousness at any time during the study. In this case, it should be reported as an adverse event.

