9.2.1.3 Analysis of Safety

All safety analyses will be performed on the Safety Population. Safety data will be subject to clinical review and summarized by appropriate descriptive statistics. A DSMB will be assigned to monitor safety on an ongoing basis throughout the study.

Analyses will be based on adverse events, vital signs, clinical laboratory assessments, and ECGs. Safety analyses will be descriptive and will be presented in tabular format with the appropriate summary statistics.

A TEAE is defined as an adverse event started on or after the administration of study drug. The number and percentage of patients with TEAEs will be tabulated by system organ class, preferred term, and by severity and relationship to treatment. Serious adverse events and adverse events leading to discontinuation from study drug will be summarized. Listings will also be provided for SAEs and adverse events leading to discontinuation of study drug.

Descriptive statistics will be provided for clinical laboratory data for both actual values and changes from baseline over time.

Descriptive statistics will be provided for vital sign data presented as both actual values and changes from baseline over time.

Abnormal physical examination findings will be listed.

Descriptive statistics will be provided for ECG interval data and presented as both actual values and changes from baseline.

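### The TEAE definition uses start date only, so an adverse event recorded between consent and first dose that worsens on drug is left out of the TEAE summaries

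*SAP*

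**What the plan says.** **Definition.** SAP 7.6.1 states that TEAEs "are defined as AEs that start on or after the administration of study drug". Protocol 9.2.1.3 agrees: "A TEAE is defined as an adverse event started on or after the administration of study drug". Neither sentence mentions worsening.

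**Capture.** Recording begins before dosing. In the SAP, "AEs will be captured from the date of informed consent through study completion". In Protocol 8.1, adverse events "will be monitored and documented from the time of informed consent until study participation is complete".

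**Re-reporting.** Protocol 8.1 has one general rule on change: "Any medical condition already present at Screening should not be reported as an adverse event unless" it, or its signs or symptoms at Baseline, should become more or less severe or serious during the study, in which case an adverse event is to be reported. A second rule in the same section deals with laboratory and other examination findings. They are reportable if clinically significant and new, or if present at Screening and significantly worse later.

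**Causality.** Protocol 8.1.3 judges relatedness from the timing of either the occurrence or the worsening of the event.

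**Outputs.** SAP 7.6.1 builds the following on the TEAE definition: the tables by system organ class and preferred term, by worst grade and by relatedness, the treatment-emergent SAE lines, and the discontinuation table and listing. Not restricted to TEAEs are any AEs, all SAEs, AEs leading to death and the full listing.

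**The concern.** A definition that looks only at the start date fits when recording begins at first dose. Here recording begins at consent, in acutely ill patients, so some adverse event records will carry a pre-dose start date. Where such an event deteriorates on drug, the deterioration is what a safety table exists to show, and the rule leaves it out.

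Safety is part of the primary objective (SAP 2.1.1), and the number of patients with TEAEs is a listed secondary parameter (SAP 6.2). For an event with a known pre-dose start, the omission can only lower the TEAE counts. In a single-arm study of about 15 patients, readers will rely on those tabulated counts.

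**Working it through.** The plan states no figure on this point, so there is none to reproduce. The check is textual, with simple arithmetic for scale.

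**1. Can a pre-dose adverse event record exist?** Yes. Capture starts at consent. For Screening, "Screening procedures must occur within a 120-hour window (for patients with candidemia) or 168-hour window" applies, the longer one being for invasive candidiasis without candidemia. Then "The initiation of the first dose of APX001 must occur within 12 hours of qualification for the study". The outer limits are 120 + 12 = 132 hours and 168 + 12 = 180 hours. These are loose upper bounds. Protocol 3.1 and Appendix A (footnote a) run the clock from collection of the standard-of-care sample, and Protocol 6.2 places that sample before consent. The interval from consent to first dose is therefore shorter.

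**2. How is each kind of event classified if it worsens on drug?**

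| Event | Rule that applies | Enters TEAE tables? |
|---|---|---|
| Condition present at Screening | Protocol 8.1: reportable once it changes | Yes, if dated from the worsening (the documents do not state the date) |
| Laboratory abnormality present at Screening | Protocol 8.1: reportable if it significantly worsens | Yes, on the same assumption; also in the SAP 7.6.2 shift or liver-threshold tables where the analyte is covered |
| Adverse event with missing or inconclusive dates | SAP 7.1.2: counted as treatment-emergent by default | Yes |
| Adverse event with a known start between consent and first dose, kept as one record | SAP 7.6.1: start date | **No** |

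Only the last row falls through. A symptom present at Screening that worsens on drug is counted. The same symptom starting a day after consent and worsening identically is not.

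**3. Which outputs lose it?**
- The TEAE table, and the worst-grade tables for all and for drug-related TEAEs.
- The drug-related TEAE table, even if the investigator judged the event related because it worsened (Protocol 8.1.3).
- The treatment-emergent SAE lines, if it became serious on drug. It stays in the all-SAE summary.
- The discontinuation table and its listing, if it led to stopping the drug. Protocol 9.2.1.3 promises both for adverse events leading to discontinuation, without restricting them to TEAEs. SAP 7.6.1 narrows them to TEAEs, while SAP 9 declares no changes from the protocol.

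**4. Size.** Take N = 15 (SAP 5: about 15, not derived from a calculation). Let x be the number of patients whose only qualifying event in a given table is of this kind. The rate omitted is x/15, with exact (Clopper-Pearson) 95% limits:
- x = 1: 1/15 = 6.7% (0.2 to 31.9)
- x = 2: 2/15 = 13.3% (1.7 to 40.5)
- x = 3: 3/15 = 20.0% (4.3 to 48.1)

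The documents give no frequency, so the chance p that a patient is affected in this sense is an assumption. With independent patients, the expected number is 15p and the chance of at least one is 1 − (1 − p)^15:
- p = 5%: 0.75 expected, 53.7%
- p = 10%: 1.5 expected, 79.4%
- p = 20%: 3.0 expected, 96.5%
- p = 30%: 4.5 expected, 99.5%

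**The case against.** The best reply is that the rest of the plan already covers most of this, and much of that reply stands.

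- **Laboratory events.** A reader might infer that a mild transaminase rise at screening that becomes severe on drug would vanish. The documents do not support that. Protocol 8.1 says an abnormal but not clinically significant value is not an adverse event, so there would normally be no pre-dose record. Significant worsening is reportable. SAP 7.6.2 tabulates liver thresholds and shifts whatever the TEAE status.
- **The worsening rule.** A reader might infer that it covers Screening conditions only. Its wording also names Baseline, which is pre-dose on Day 1, and some sites might take it as calling for a new report. But the sentence opens with conditions that are not to be reported until they change. It does not clearly ask for a second record of an event already reported after consent.
- **Visibility.** The events are not lost from the report. They remain in the any-AE, all-SAE and death outputs and in the full listing, and about 15 patients can be read case by case. The study stopping rule (Protocol 8.5.1) refers to related adverse events, not TEAEs.
- **Direction.** It would be too strong to say that the plan's date handling always favours the drug, because SAP 7.1.2 sends unclear dates the other way. The result is odd, though: an event with an unknown date is treated more conservatively than one known to have worsened on drug.
- **Size.** A patient with another qualifying TEAE changes nothing, and over up to 42 days of treatment and 4 weeks of follow-up many may have one.
- **Unseen documents.** The eCRF instructions or the separate programming specifications (SAP 10) may already handle worsening. The claim is about these two documents only.

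None of this puts an event with a known pre-dose start that worsens on drug into the TEAE tables.

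**Conclusion.** The point holds in a limited form. As written, both definitions exclude an adverse event that starts between consent and first dose, stays one record, and increases in grade or becomes serious on drug. This is a stated rule that can produce a wrong count, and it sits badly with the causality wording and with the protocol's promised summary of discontinuations.

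The practical weight falls on symptoms. Protocol 1.2 names headache, dizziness, fatigue, nausea and vomiting as potential adverse events. These have no shift table, and examination findings are only listed (SAP 7.6.5), so the TEAE tables are their main summary. If the any-TEAE rate is already high in this population, the effect will show mostly in the related, worst-grade and discontinuation tables.

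The effect is at most 6.7 points per affected patient, assuming about 15 treated patients and no other qualifying TEAE in that patient. How many patients would be affected cannot be known from the documents.

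**What to change.** In SAP 7.6.1 and Protocol 9.2.1.3, define a TEAE as an adverse event that starts on or after the first dose, or that starts before it and increases in CTCAE grade or becomes serious on or after it. Instruct sites to enter such a worsening as a new adverse event with its own start date, so that the classification can be programmed from the data.

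At the same time, either let the SAP discontinuation table and listing cover all adverse events, as the protocol says, or record the narrowing in SAP 9.

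The cost is one sentence in each document and one eCRF instruction. Design, sample size and patient care do not change. TEAE counts may rise slightly. Event counts in the any-AE overview will include both records, but patient counts are protected because SAP 7.6.1 counts a patient once per preferred term. Any worsening already held within a single record would need a data query to obtain its date.

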### **7.6.2 Clinical Laboratory Tests**

Central laboratory test results (chemistry, hematology, coagulation, and urinalysis) at each scheduled visit and change from baseline will be summarized with descriptive statistics.

Shift tables from baseline to each scheduled post-baseline visit will be provided for selected chemistry parameters (ALT, AST, ALP, Total Bilirubin, Creatinine, and Creatinine Kinase) and hematology parameters (Hematocrit, Hemoglobin, Platelets, White blood cell count and differential). For chemistry parameters, the following categories will be used: < the lower limit

of normal (LLN), normal,  $>\text{ULN}$  to  $\leq 2 \times \text{ULN}$ ,  $>2 \times \text{ULN}$  to  $\leq 3 \times \text{ULN}$ ,  $>3 \times \text{ULN}$  to  $\leq 5 \times \text{ULN}$ ,  $>5 \times \text{ULN}$ , and missing. For hematology parameters, the following categories will be used: low, normal, high, and missing.

The number and percentage of patients with the following potentially clinically significant abnormal liver function tests at any post-baseline visit will be summarized:

- $\text{ALT} \geq 3 \times \text{ULN}$
- $\text{ALT} \geq 5 \times \text{ULN}$
- $\text{ALT} \geq 10 \times \text{ULN}$
- $\text{AST} \geq 3 \times \text{ULN}$
- $\text{AST} \geq 5 \times \text{ULN}$
- $\text{AST} \geq 10 \times \text{ULN}$
- $\text{ALT}$  or  $\text{AST} \geq 3 \times \text{ULN}$
- Total Bilirubin  $>1.5 \times \text{ULN}$
- Total Bilirubin  $>2 \times \text{ULN}$
- $\text{ALP} \geq 1.5 \times \text{ULN}$
- $\text{ALP} \geq 2 \times \text{ULN}$
- $\text{ALT}$  or  $\text{AST} \geq 3 \times \text{ULN}$  and Total Bilirubin  $>1.5 \times \text{ULN}$
- $\text{ALT}$  or  $\text{AST} \geq 3 \times \text{ULN}$  and Total Bilirubin  $>2 \times \text{ULN}$
- Potential Hy's Law cases:  $\text{ALT}$  or  $\text{AST} \geq 3 \times \text{ULN}$  and Total Bilirubin  $>2 \times \text{ULN}$ , and  $\text{ALP} \leq 2 \times \text{ULN}$

A listing of patients with any post-baseline clinically significant abnormal liver function tests will be presented.

All clinical laboratory data will be listed. Values outside the normal ranges will be flagged.

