Clinically significant abnormal laboratory or other examination (e.g., ECG) findings that are detected during the study or are present at Screening and significantly worsen during the study should be reported as adverse events. The Investigator will exercise his or her medical and scientific judgment in deciding whether an abnormal laboratory finding or other abnormal assessment is clinically significant. Clinically significant abnormal laboratory values occurring during the clinical study will be followed until repeat tests return to normal, stabilize, or are no longer clinically significant. Any abnormal test that is determined to be an error does not require reporting as an adverse event. A laboratory finding that is abnormal but not clinically significant (e.g., does not warrant intervention) is not considered an adverse event.

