8.7 Clinical Laboratory Evaluations

Screening laboratory assessments to determine eligibility will be performed at the local laboratory and may have been collected as SOC within the previous 24 hours. Laboratory assessments collected after Screening will be sent to the central laboratory for analysis.

Clinical laboratory assessments (serum chemistry, hematology, coagulation, and urinalysis) will occur at Baseline (pre-dose), twice weekly during Study Drug Treatment, at EOST, and at 2 and 4 weeks after EOST, or Early Termination. If clinically indicated and at the discretion of the Investigator, or if a suspected adverse event is identified, clinical laboratory assessments may be conducted at any time during the study and compared to Baseline. See [Appendix B](#) for a complete list of clinical laboratory analytes.

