##### **6.4.5.2 Clinical Laboratory Evaluations**

Screening laboratory assessments to determine eligibility will be performed at the local laboratory and may have been collected as SOC within the previous 24 hours. Laboratory assessments collected after Screening will be sent to the central laboratory for analysis.

Clinical laboratory assessments (serum chemistry, hematology, coagulation, and urinalysis) will occur at Baseline (pre-dose), twice weekly during Study Drug Treatment, at EOST, and at 2 and 4 weeks after EOST, or Early Termination. If clinically indicated and at the discretion of the Investigator, or if a suspected adverse event is identified, clinical laboratory assessments may be conducted at any time during the study and compared to Baseline. The following is a complete list of clinical laboratory analytes.

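### SAP 7.6.2 ties laboratory tables to scheduled visits, so for creatinine, creatine kinase and haematology no table shows unscheduled results or a patient's worst value, and peak abnormality can be understated

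*SAP*

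**What the plan says.** SAP 7.6.2 plans five kinds of laboratory output.

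- **Descriptive summaries:** "Central laboratory test results (chemistry, hematology, coagulation, and urinalysis) at each scheduled visit and change from baseline will be summarized with descriptive statistics".
- **Shift tables:** "Shift tables from baseline to each scheduled post-baseline visit will be provided for selected chemistry parameters". The chemistry parameters are ALT, AST, ALP, total bilirubin, creatinine and creatine kinase (printed there as creatinine kinase; the SAP's analyte list has creatine kinase). Haematocrit, haemoglobin, platelets and white cell count with differential follow the same by-visit rule.
- **Liver threshold counts:** patients with potentially clinically significant "abnormal liver function tests at any post-baseline visit will be summarized". This wording is not limited to scheduled visits. It covers ALT, AST, bilirubin, ALP and potential Hy's Law cases only.
- **Liver listing:** patients with such liver abnormalities after baseline.
- **Full listing:** "All clinical laboratory data will be listed. Values outside the normal ranges will be flagged".

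Both documents foresee tests outside the schedule. SAP 6.4.5.2 says that when clinically indicated, "or if a suspected adverse event is identified, clinical laboratory assessments may be conducted at any time during the study and compared to Baseline". Protocol 8.7 has the same provision.

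There is also an adverse event route. Under Protocol 8.1, clinically significant abnormal laboratory findings "that are detected during the study or are present at Screening and significantly worsen during the study should be reported as adverse events". SAP 7.6.1 then counts patients with TEAEs by system organ class and preferred term, and by worst grade.

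**The concern.** A test taken because something seems wrong is more likely than a routine one to show an abnormal value. As SAP 7.6.2 is worded, such a result has no place in the by-visit summaries or the shift tables unless it happens to belong to a scheduled visit. For liver tests the any-visit count makes up for this. For creatinine, creatine kinase and haematology nothing among the laboratory tables does.

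There is a second gap even if no extra test is ever drawn. The shift tables are organised by visit, so they do not say how many patients ever moved above the upper limit of normal for creatinine, or ever fell to low platelets.

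At stake is the completeness of the laboratory safety summary in a study whose primary objective includes safety. The primary efficacy result and the analysis populations are not affected.

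**Working it through.** The plan states no figure to reproduce, so the check is to trace where an unscheduled result would appear.

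| Planned output | Liver tests | Creatinine, creatine kinase, haematology |
|---|---|---|
| Descriptive summary by visit (SAP 7.6.2) | scheduled only | scheduled only |
| Shift table by visit (SAP 7.6.2) | scheduled only | scheduled only |
| Patient count at any post-baseline visit (SAP 7.6.2) | yes | none |
| Flagged listing (SAP 7.6.2) | yes | yes |
| TEAE tables (SAP 7.6.1) | if reported as an adverse event | if reported as an adverse event |

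The right-hand column shows the gap: the only outputs open to an unscheduled value are a listing, which gives no count, and the TEAE tables, which depend on the event having been reported.

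**Number of time points.** At the 42-day maximum there are 2 × 6 = 12 twice-weekly draws, plus EOST, plus two follow-up visits: 12 + 1 + 2 = 15 scheduled post-baseline time points. This is an upper limit; patients treated for less time have fewer. One patient's abnormality can be spread over as many of these as it lasts.

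**How easily a short abnormality falls between draws.** Inputs: draws are twice weekly, which is 3.5 days apart if evenly spaced. Protocol 6.4.2 gives a window of 2 to 4 days, read here as the spacing. Assumptions: onset is uniform over the interval, and the duration d is chosen for illustration. With spacing g, the chance of missing every scheduled draw is max(0, 1 − d/g).

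| Duration d | g = 2 days | g = 3.5 days | g = 4 days |
|---|---|---|---|
| 1 day | 1 − 1/2 = 50% | 1 − 1/3.5 = 71% | 1 − 1/4 = 75% |
| 2 days | 0% | 1 − 2/3.5 = 43% | 1 − 2/4 = 50% |
| 3 days | 0% | 1 − 3/3.5 = 14% | 1 − 3/4 = 25% |
| 4 days or more | 0% | 0% | 0% |

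Appendix A footnote b words the outpatient window as ±2 days, under which a gap could exceed 4 days and the chances would rise.

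**What these figures do not give.** They describe overlap with a scheduled draw, not the loss caused by the SAP rule. A loss also needs three things: an unscheduled sample was taken during the abnormality, it fell in a worse shift category than any scheduled value, and it was not reported as an adverse event. The documents give no rate for any of these, so the product cannot be formed. An abnormality that no sample caught is lost under any table. For scale only, one patient in about 15 is 1/15 = 6.7 percentage points.

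**The case against.** The strongest objection is that the adverse event route is built for these values. Protocol 8.1 includes laboratory variables among adverse events and requires clinically significant findings to be reported. Protocol 8.1.3 has events graded by CTCAE. SAP 7.6.1 counts each patient once per preferred term and tabulates worst grade. None of this depends on the visit schedule, and a test drawn on suspicion of an adverse event is the kind of result most likely to be recorded as one. All values are also listed and flagged, and about 15 patients' listings can be read in full. Protocol 9.2.1.3 asks only for descriptive statistics of values and changes, so the shift tables already exceed it.

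Most of this stands, and it rules out a stronger reading that a reader might infer: that toxicity is under-reported, that for-cause results reach only the listings, or that no patient-level incidence of renal, muscle or haematological abnormality will exist. The documents do not support any of these, because clinically significant findings are to be counted per patient in the TEAE tables.

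The objection does not close the gap entirely. Protocol 8.1 excludes from adverse events an abnormal value judged not clinically significant, and it asks investigators to record a disease or syndrome in preference to its separate signs where possible. The TEAE tables therefore pass through investigator judgement in an open-label study, whereas a laboratory table does not. A listing can be read, but it gives no incidence.

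It may also be said that the separate programming specifications named in SAP section 10 could assign unscheduled results to visits. That cannot be checked here. The SAP states no such rule, and assigning results to visits would still not produce a worst-value table.

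**Conclusion.** The point holds in a limited form. For creatinine, creatine kinase and haematology, SAP 7.6.2 plans no table that includes unscheduled results as laboratory data and none that shows each patient's worst value. The laboratory tables can therefore understate peak abnormality. What is exposed is mainly abnormality not recorded as an adverse event: values judged not clinically significant, and peaks between scheduled visits that exceed the values seen at those visits.

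The size cannot be computed from the documents. The chances of falling between draws are illustrations that rest on assumed durations, uniform onset and assumed spacing. They should not be read as an expected loss. Nor is 6.7 percentage points an expected effect; it is only the weight of one patient in about 15.

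The verdict rests on reading the scheduled-visit wording as it stands, with no unseen rule bringing unscheduled results into the tables. The gap does not undermine the study. It is worth closing because safety is in the primary objective, the SAP already gives the liver tests a count that is not tied to the schedule, and the change is small.

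**What to change.** In SAP 7.6.2 add, for the same parameters as the existing shift tables, one shift table from baseline to the worst post-baseline value. Use scheduled and unscheduled results. For haematology, give the worst value in both directions, lowest and highest. Keep the by-visit tables. Add a sentence on how unscheduled results are handled in the by-visit summaries, so that this does not rest on the programming specifications alone.

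The cost is a sentence or two in the SAP and one extra table from data already collected. SAP section 1 says the plan is finalised before database lock, which is the time to do it. The downside is that the laboratory profile may look slightly less favourable. No clinical rule or study procedure changes.
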